If participants instill *Lactobacillus* at any time during the intervention phase, and after *Lactobacillus* instillation reports a UTI as an Adverse Event (AE) we will request their urinalysis and urine culture results to attempt to determine if *Lactobacillus* might have been the cause of the UTI. If determined necessary by the PI, Co-PI and/or DSMB other AEs reported could require retrieval of medical records.

Phase III: Pilot Study of Multiple (up to 2) *Lactobacillus* Bladder Instillations

We will recruit 30 persons in whom we will collect urine up to 18 timepoints (up to monthly for the first year when not experiencing symptoms, up to two times when subject experience urinary symptoms, follow-up after either *Lactobacillus* treatment or antibiotics, and three (3) months into the six (6) months follow-up) in order to **estimate the strength of the associations between successful implementation of the probiotic self-management program and urinary symptoms, bladder inflammation, and the urine microbiome.** We will conduct an 18-month study in which each participant will serve as his/her own control through 3 phases of study: 6-months usual care (baseline), 6-months probiotic intervention, and 6-months follow-up
Study Design: We will recruit N=30 subjects with neuropathic bladder who will contribute urine samples for analyses.

Clinical Setting: MedStar National Rehabilitation Hospital and Children's National Medical Center.

Target Enrollment: 30 adult subjects at least 1-year post-injury and 18 years of age with SCI/MS or at least 18 years of age with SB

Recruitment Strategy: SCI/MS and SB subjects will be enrolled with assistance from United Spinal Association. Additionally, we will query the MedStar National Rehabilitation Hospital inpatient service, the 40+ MedStar National Rehabilitation Network outpatient sites, various MedStar Network databases, and the CNMC Spina Bifida database. Databases will be queried for participants who meet the eligibility criteria and have already provided HIPAA authorization and consent to be contacted for future research. Announcements and IRB-approved flyers will be posted on the United Spinal Association and study websites and at participating institutions.

Informed Consent: Consent will be obtained by the PI, Study Coordinator, or Research Assistant. All project staff are currently CITI certified and have passed all requirements for HIPAA certifications.

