After 6 months of baseline data collection the intervention phase will begin. Prior to implementing the intervention protocol, participants will provide study staff with a urine sample either at MedStar NRH, CNMC, or when possible, the study RA will meet with the participant at a mutually convenient location. After urine sample is collected, study participants will follow the study protocol and complete USQ-NB weekly. If/when urinary symptoms occur, they will be instructed to follow the SMP_{PRO} protocol to determine whether to initiate intravesicular *Lactobacillus* instillation or be evaluated by a physician. The self-management protocol (SMP_{PRO}) will also direct them to discontinue *Lactobacillus* instillation or be evaluated by a physician if symptoms remit, persist or worsen. If participants are directed by the self-management protocol to seek medical attention or s/he feels the need for medical evaluation, s/he will be advised to obtain care as they typically would by their health care provider. Participants will be supplied with letters to be brought to their health care provider notifying them of the study and requesting sharing of urinalysis and urine culture results with the research team. A verified UTI will include those that resulted in antibiotic treatment by a health care professional. An additional urine sample for metagenomics will either be left with the health care provider for pick up by the research team, brought to the research site, or obtained by the RA at a mutually convenient site. If participant is treating urinary symptoms at home with *Lactobacillus*, a urine sample will be dropped off either at MedStar NRH, CNMC or when possible, the study RA will meet with the participant at a mutually convenient location.

The Impact of Self-Management with Probiotics on Urinary Symptoms and the Urine Microbiome in Individuals with Spinal Cord Injury and Spina Bifida Protocol

5/18/2017

Page 8 of 17

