For the intravesicular *Lactobacillus* instillation, the contents of 1 *Lactobacillus* capsule will be mixed into 45 cc sterile 0.9% saline (adult bladder volume is 450cc, so this amount represents 10% of adult bladder volume). After mixing, study personnel will draw up the 45 cc of the liquid *Lactobacillus* mixture into a 60cc catheter tip syringe and instill via the intermittent catheter. For children volume is based on age (see table on page 4 of protocol). Study participant will recheck symptoms after 24 hrs (valid range 22-30 hrs) following the SMP_{PRO} protocol and either complete another *Lactobacillus* instillation or seek medical attention. If symptoms still persist 4 hrs after second instillation, study participants should seek medical attention.

Post-Intervention Follow-Up:

After completion of the 6-month patient-initiated self-management protocol intervention period, participants will monitor symptoms weekly using the USQ-NB. At the end of follow-up, we will obtain another urine sample from all participants.

Measurements:

In addition to the measurements described in Phase II the following measurements will occur for phase III;

Urine Acquisition: A 50-100 ml urine sample will be collected from each subject for (1) urinalysis and cultivation, and (2) urine microbiome by SMRT sequencing. Urine will be collected from a new, unused intermittent catheter.

Urine Preparation: Collected urine will be immediately placed at 4°C. Within 6 hours, samples will be taken to CNMC for sequencing preparation. At CNMC, urine samples will be centrifuged at 4°C, 5,000 x g for 20 minutes. The supernatant will be aliquoted in 2 ml cryotubes and frozen at -20°C. 10ml PBS will be added to the pellet with the remaining supernatant and then centrifuged (5,000xg) at 4°C for 20 minutes. The pellets and aspirated PBS wash solution will be stored at -20°C. Pellets will later be transferred for DNA isolation and SMRT sequencing.

Urinalysis: Urine samples will be assessed utilizing standard clinical microbiology semiquantitative chemical testing using commercial disposable test strips for glucose, bilirubin, ketone, specific gravity, blood pH, protein, urobilinogen, nitrite, and leukocyte esterase. After centrifuging for 5 minutes, microscopic examination for and quantification of WBCs, RBCs, epithelial cells, yeast, bacteria, *Trichomonas vaginalis*, sperm cells, mucous filaments and crystals will be performed using standard microbial techniques.

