H1. Compared with usual management, self-management of urinary symptoms with probiotics will reduce the frequency, severity and impact of urinary symptoms and UTIs (PRIMARY OUTCOMES). The goal of aim 2 is to assess the effect of *Lactobacillus* supplementation on the frequency, severity and impact of urinary symptoms and UTIs. This aim can be evaluated with all 100 participants in the SMP pilot study. We expect to find a significant difference in these primary outcomes between our three experimental timeframes (6 months prior to intervention, 6 months of SMP_{PRO} intervention, and 6 month follow-up period). Frequency of UTI will be defined as the number of verified UTIs occurring during the timeframe. Urinary symptoms will be assessed using the USQ-NB where frequency of symptoms, degree of severity, and impact on the individual, will be considered.

We will estimate the average number of symptoms on the USQ-NB endorsed (irrespective of frequency, severity and impact) across the weeks during that time frame, for each participant. Thus, each participant will have a continuous outcome (average number of USQ-NB items endorsed). We will also compute the number of verified UTIs experienced by each participant. These two outcomes are the primary outcomes for our study and analysis; they depend solely on the face validity of the USQ-NB, and on clinically verified UTIs, and so will not be affected by a failure to find or establish formal measurement properties for the USQ-NB, should any occur. They will also be less subject to any variability in participant perceptions of frequency, severity or impact, which can complicate analytic assumptions and limit power and interpretability of change that might be perceived. We will describe these features of the sample over time but will not conduct inference tests on these ratings.

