H2. Compared with usual management, self-management of urinary symptoms with probiotics will reduce bladder inflammation (Secondary outcome). For those 20 participants in the subsample giving urine samples, bladder inflammation will be measured from each urine sample using a standard white blood count (WBC) from the urinalysis. WBC counts will be obtained only at the start of each timeframe, and so can be analyzed longitudinally as continuous variables representing the 6-month pre-treatment period and the 6 month-SMP_{PRO} period. As such we plan a mixed effects linear regression model of WBC counts with time treated as the factor of interest. This analysis will assess whether WBC is significantly different from the SMP_{PRO}, and post-SMP_{PRO}, relative to the baseline pre-treatment periods.

H3. Compared with usual management, self-management of urinary symptoms with probiotics will reduce the need for antibiotics to treat UTI (Secondary outcome). The number of times antibiotics are used for each patient will be obtained from their medical records or self report. This value will be analyzed with the same three-point longitudinal mixed effects regression model with time as the factor of interest. Depending on the distribution of the outcome (i.e. given the count nature of this outcome, it may be Poisson distributed), we will utilize either linear or Poisson regression models. This analysis will assess whether there is an association between UTI rate during use of the SMP_{PRO}, and post-SMP_{PRO} exposure, relative to UTI rate during the baseline pre-treatment period.

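### H2 gives two conflicting rules for WBC sampling, and the one its model uses yields at most one post-intervention sample for two planned contrasts

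*Combined protocol and SAP*

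**What the plan says.** All references are to the combined protocol and SAP.

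- **H2, first rule:** "For those 20 participants in the subsample giving urine samples, bladder inflammation will be measured from each urine sample".
- **H2, second rule:** "WBC counts will be obtained only at the start of each timeframe, and so can be analyzed longitudinally as continuous variables". The same sentence says that the values stand for the pre-treatment and SMP_PRO periods and does not name follow-up. The mixed model is then introduced as following from this rule.
- **H2, contrasts:** WBC in the SMP_PRO period and in the post-SMP_PRO period is to be judged "relative to the baseline pre-treatment periods".
- **H1, timeframes:** differences are sought "between our three experimental timeframes (6 months prior to intervention", then six months of SMP_PRO and six months of follow-up).
- **H3, model:** "This value will be analyzed with the same three-point longitudinal mixed effects regression model with time as the factor of interest".
- **Phase III, Intervention:** "Prior to implementing the intervention protocol, participants will provide study staff with a urine sample".
- **Phase III, introduction:** urine is collected "up to monthly for the first year when not experiencing symptoms, up to two times when subject experience urinary symptoms", again after treatment, and three months into follow-up, for up to 18 timepoints. Participant Burden names urinalysis as one purpose of these samples and places the symptom samples in the intervention phase.
- **Phase III, Urinalysis:** includes "microscopic examination for and quantification of WBCs".
- **Phase III, Post-Intervention Follow-Up:** a urine sample is taken from everyone at the end of follow-up.
- **Urine subsample size:** 20 in H2, 30 in the Phase III design, 50 in H4.

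**The concern.** The two H2 rules stand in adjacent sentences and cannot both be true when up to 18 samples with urinalysis are planned. The model rests on the narrower rule, which samples each period at its start. For the intervention period, that is the moment before anything has been done.

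An analyst who follows the rule and labels month 6 as SMP_PRO would report a coefficient that looks valid but contains no exposure. Any difference would reflect time alone, and a null could be misread as no effect on inflammation. A second analyst who follows the other sentence would use in-period samples and could get a different answer. Both would be following the plan.

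**Working it through.** H2 gives no power, effect size, SD or alpha, so there is no figure of its own to reproduce. The check is a count of sampling times, followed by an illustration on stated assumptions.

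**1. Start-of-timeframe samples.** Three six-month timeframes start at months 0, 6 and 12.

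| Sample | Position | After any intervention time? |
|---|---|---|
| Month 0 | start of usual care | no |
| Month 6 | before the intervention is implemented | no |
| Month 12 | start of follow-up; not explicitly scheduled | yes, if taken |

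So 1 of 3 start samples follows any intervention time, or 0 if month 12 is not sampled.

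**2. Two contrasts, two possible labellings.** The plan ties no specific sample to the SMP_PRO label.

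- *Months 0, 6, 12 = baseline, SMP_PRO, post-SMP_PRO.* This fits the three timeframes and the three-point model mentioned in H3. SMP_PRO versus baseline is then month 6 minus month 0, with 0 of 26 intervention weeks before either value. Post-SMP_PRO versus baseline is month 12 minus month 0. That can carry an effect, but it describes the end of the intervention, not follow-up.
- *Months 0 and 6 = pre-treatment, month 12 = SMP_PRO.* Post-SMP_PRO then has no start-of-timeframe sample.

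**3. Size under the first labelling.** Assumptions not in the documents: random-intercept model, between- and within-subject SD 1, constant effect of -0.8 present only after the month-6 sample, two-sided alpha 0.05, no time drift, complete data, 20,000 simulated trials per N.

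| N | Month 6 - month 0: mean, rejection | Month 12 - month 0: mean, rejection |
|---|---|---|
| 20 | 0.00, 4.9% | -0.80, 69% |
| 30 | 0.00, 5.1% | -0.80, 86% |
| 50 | 0.00, 4.9% | -0.80, 98% |

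Hand check for the last column at N = 20: the standard error is √(2/20) = 0.316, so the noncentrality is 0.8/0.316 = 2.53 on 2 × 19 = 38 degrees of freedom. The critical value is 2.02 and the power is 69%.

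**4. What the rule leaves unused.** Assume that 4 of the 18 samples are symptom-linked (2 symptom + 2 post-treatment). Then 18 - 4 = 14 are routine: 13 monthly (months 0-12) + 1 follow-up, or 12 monthly (months 0-11) + 2 follow-up. The start-only rule uses at most 3 of these 14 and none from months 7-11.

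**5. What the other rule would give.** With monthly samples at months 0-12 plus month 15, there are 7 baseline samples (months 0-6), 6 SMP_PRO samples (months 7-12) and 1 follow-up sample. Each contrast then has data from the period it names. Adding month 18 makes 15 routine samples, and 15 + 4 = 19 exceeds the cap of 18. A month-12 sample and both follow-up samples therefore cannot all be taken at full monthly frequency.

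**6. Subsample size.** For a contrast that does contain exposure, the paired standardized difference detectable with 80% power (noncentral t, two-sided alpha 0.05, one sample per period, complete pairs) is 0.66, 0.53 and 0.40 at N = 20, 30 and 50.

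**The case against.** The strongest reply is that this is a wording conflict and the design itself is sound. Monthly urinalysis with WBC quantification is planned through year 1, so in-period values can exist whichever sentence the SAP keeps. With samples at months 0, 6 and 12 both contrasts can be fitted. The three-point phrase belongs to H3 and labels no urine sample, and H2's plural reference to baseline periods is compatible with months 0 and 6 both being pre-treatment. The simulated 5% is true by construction. The outcome is secondary, in a pilot.

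Much of this is fair. Data collection can supply what is needed, and the defect lies in what the coefficients mean, since they can be computed. It does not remove the problem. The analysis text says that WBC is obtained only at timeframe starts, and neither labelling then gives valid data for both contrasts. The clause naming two periods assigns no sample to either and sits badly with a post-SMP_PRO contrast.

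One refinement stands. If the effect varies between people (assumed SD 1), the pooled residual variance rises and month-6 rejection falls to about 2.5%, with month-12 power of 57%, 74% and 92%. Rejection equal to alpha therefore holds for a constant effect, and variation makes the contrast less informative still. It is also fair that the subsample size is a separate inconsistency, that follow-up timing is unclear rather than contradictory, and that one named sample per period would be another way to repair the rule.

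**Conclusion.** The concern holds. As written, H2 is contradictory, and the rule on which its model rests cannot validly support both planned contrasts. This follows from the documents' own timeline and needs no assumed effect size; the power figures only illustrate it. The claim that the SMP_PRO contrast contains no exposure depends on month 6 carrying that label. The alternative labelling moves the gap to post-SMP_PRO. Without a month-12 sample, neither contrast has a post-exposure value under the rule. The point should be fixed before analysis. It is confined to a secondary outcome, although bladder inflammation is a stated Phase III objective.

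**What to change.** 1. Delete the start-only sentence and take WBC from the planned urinalyses.
2. Assign samples to periods by date: up to and including the pre-intervention month-6 sample is baseline; later samples through month 12 are SMP_PRO (probiotic offered, not necessarily used); anything after that is post-SMP_PRO.
3. State how repeated values enter the model: period means, or all values with a stated within-person correlation structure.
4. Pre-specify whether symptom-triggered and post-treatment samples belong in the main contrast or in a sensitivity analysis. Leaving them out keeps sampling alike across periods but limits the main contrast to symptom-free WBC, a state the intervention may itself change. Including them covers treated episodes but adds symptomatic samples to one period only.
5. State whether a month-12 sample is taken and whether follow-up urine is at three months, at the end, or both, within the cap of 18.
6. Reconcile the urine subsample size (20, 30 or 50).

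The cost is SAP wording and one clarified sampling schedule. No new samples are needed if month 12 is one of the monthly collections.

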Inclusion criteria for participants with SCI/SB/MS includes: 1) age \geq 18 years; 2) SCI/SB/MS; 3) neuropathic bladder at least 1-year duration, as determined by the attending physician; 4) utilizing intermittent catheterization for bladder management; 5) a history of 2 or more UTIs in the past year; 6) community dwelling, 7) Enrollment in Phase II

Exclusion Criteria: Study candidates with the following will be excluded: 1) known genitourinary pathology beyond neuropathic bladder (i.e., vesicoureteral reflux, bladder or kidney stones, etc.); 2) use of prophylactic antibiotics; 3) instillation of intravesicular agents to reduce UTI (i.e., gentamycin); 4) psychologic or psychiatric conditions influencing the ability to follow instructions; 5) participation in another study in which results would be confounded; 6) pregnant or breastfeeding; 7) individuals with a history of acquired or genetic immunodeficiencies; active, acute or chronic serious infections (i.g., viral hepatitis, HIV/AIDS); 8) individuals with cancer/autoimmune disorders; 9) serious allergy to any component or excipients in the live bacterial combination product; 10) no change in neurologic status in the previous 2 weeks; 11) taken antibiotic for any reason in the previous 2 weeks; 12) any patient with history of sensitivity or allergy to ampicillin or tetracycline; and 13) current urinary tract infection or urinary tract infection within the previous 2 weeks (as defined by Infectious Diseases Society of America CAUTI Guidelines, 2010 14) Not enrolled in Phase II. According to the Infectious Disease Society of America Guidelines for Diagnosis of Catheter-Associated UTI, the presence of the

The Impact of Self-Management with Probiotics on Urinary Symptoms and the Urine Microbiome in Individuals with Spinal Cord Injury and Spina Bifida Protocol

5/18/2017

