following urinary symptoms is required for UTI diagnosis in patients using intermittent catheterization: new onset or worsening fever, rigors, altered mental status, malaise, lethargy with no other identified cause, flank pain, costovertebral angle tenderness, acute hematuria, pelvic discomfort, increased spasticity, autonomic dysreflexia or sense of unease. The Guidelines specifically state that “the presence or absence of odorous or cloudy urine should NOT be used as an indication for urine culture or antimicrobial therapy” and “the presence, absence or degree of pyuria should NOT be interpreted as an indication for antimicrobial treatment.” If a subject presents with any of these symptoms and there are $\geq 10^3$ cfu/hpf bacterial growth on urine culture, the subject will be excluded and treated for a UTI according to clinical best practice.

Participant Burden:

Urine samples for urinalysis, urine culture and metagenomic sequencing will be obtained at up to monthly for the first year of study participation when not experiencing symptoms, at up to 2 occurrences of urinary symptoms during SMP_{PRO} intervention phase, and follow-up after either lactobacillus treatment or antibiotics and at follow-up, for a total of up to 18 samples per patient depending on the frequency with which urinary symptoms are experienced. When possible, our Research Assistant will meet with the patient at a mutually convenient location.

Baseline Data Collection:

Per IRB protocol # 2014-211 phase II, after consent, participants will complete the Health History Questionnaire, Urinary Symptom Questionnaire, In addition to questionnaires, all participants will provide a urine sample using sterile catheterization techniques. Thereafter, participants will complete the Urinary Symptom Questionnaire weekly.

Intervention:

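### H2 compares later WBC values with an entry-screened baseline, although later samples carry no such screen, and lets a pre-exposure sample stand for the SMP period

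*Combined protocol and SAP*

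**What the plan says.** The H2 paragraph (bladder inflammation, secondary outcome) states that "WBC counts will be obtained only at the start of each timeframe". The analysis is a "mixed effects linear regression model of WBC counts with time treated as the factor of interest"; no term for symptoms, recent UTI or antibiotic use is named. Its aim is given as: "This analysis will assess whether WBC is significantly different from the SMP_{PRO}, and post-SMP_{PRO}, relative to the baseline pre-treatment periods". The same paragraph also says that "bladder inflammation will be measured from each urine sample using a standard white blood count (WBC) from the urinalysis", and it describes the values as "continuous variables representing the 6-month pre-treatment period and the 6 month-SMP_{PRO} period". That is two timeframes, where the contrast needs three.

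The Phase III sections set out when urine is taken:

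- **Exclusion Criteria:** a candidate is ineligible with a current UTI, with a UTI in the previous 2 weeks, or having "taken antibiotic for any reason in the previous 2 weeks".
- **Baseline Data Collection:** every participant gives urine after consent.
- **Participant Burden:** routine samples are taken "up to monthly for the first year of study participation when not experiencing symptoms". The opening paragraph of Phase III gives the same rule.
- **Intervention:** after six months, "Prior to implementing the intervention protocol, participants will provide study staff with a urine sample". That sentence sets no condition on symptoms, UTI or antibiotics.
- **Follow-up:** the opening paragraph of Phase III places a sample three months into follow-up (month 15). Post-Intervention Follow-Up places one at the end (month 18). Neither states a symptom condition.

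**The concern.** A recent infection and a recent antibiotic can both plausibly move urinary WBC. The entry screen is meant to keep both out of the reference value, and nothing keeps them out of the values compared with it. A participant treated for a UTI within the past two weeks could not have entered the study. Once enrolled and free of symptoms, the same person could give a month-6 or month-12 sample. Each participant is his or her own control and there is no concurrent arm, so any shift from this source goes into the time effect, which H2 reads as the effect of the SMP.

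A second problem lies in the same sentence of H2. A value taken at the start of a timeframe describes what came before it. For the SMP timeframe, what came before is usual care.

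At stake is whether H2 can be interpreted at all. A difference could appear without any SMP effect, or a real one could be masked.

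**Working it through.** H2 has no stated sample size calculation, power or effect size, so there is no figure to reproduce. The check has three parts.

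**1. The sampling condition at each start of timeframe (months 0, 6 and 12)**

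- *Month 0:* follows the 2-week UTI and antibiotic exclusion. The interval between screening and the sample is not stated.
- *Month 6:* either one of the symptom-free first-year samples, or a separate sample with no condition. The cap of 18 samples per patient does not decide between them. One count is 13 monthly (months 0 to 12) + 2 symptomatic + 2 post-treatment + 1 follow-up = 18. Another is 12 monthly + 1 separate month-6 sample + 2 + 2 + 1 = 18.
- *Month 12:* no dedicated sample is named. The only source is the last monthly sample, which is symptom-free.

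On either reading of month 6, the 2-week condition attaches to month 0 alone.

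**2. Exposure at each point**

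Months 0 and 6 both precede SMP use, so the contrast of month 6 with month 0 contains no SMP effect whatever the sampling rule. Only month 12 follows exposure, and by H2's labelling it opens the post-SMP timeframe.

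**3. How many later samples the entry UTI rule would have barred**

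Inputs: at least 2 UTIs in the past year (Phase III inclusion criteria); one UTI per month, or 6 in six months (Power calculation); 20 participants (H2) or 30 (Phase III target enrollment). Assumption: UTIs follow a Poisson process and the sampling day is arbitrary.

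P(at least one UTI in 14 days) = 1 − exp(−daily rate × 14)

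- At 2 per year: 1 − exp(−2 × 14/365.25) = 1 − exp(−0.077) = 0.074, which is 1.5 of 20 or 2.2 of 30.
- At 6 per six months: 1 − exp(−6 × 14/182.6) = 1 − exp(−0.460) = 0.369, which is 7.4 of 20 or 11.1 of 30.

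As an illustration only, suppose WBC in the affected samples is higher by D standard deviations. The mean then shifts by p × D:

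| UTI rate | D = 0.5 | D = 1 | D = 2 |
|---|---|---|---|
| 2 per year | 0.04 SD | 0.07 SD | 0.15 SD |
| 1 per month | 0.18 SD | 0.37 SD | 0.74 SD |

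A paired comparison of month 6 with month 0 was simulated with no SMP effect, D = 1, an assumed within-person correlation of 0.5 and a two-sided 5% level. It rejects in about 6% (n = 20) to 7% (n = 30) of trials at 2 UTIs per year, and in 29% to 43% at one per month. These figures treat month 6 as unrestricted. If the symptom-free rule covers it, they are too high. If recent antibiotics lower WBC, the sign reverses.

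**The case against.** The strongest case on the other side concerns size, and most of it stands.

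- One UTI per month is a conditional input to a power calculation, not a forecast for Phase III. The only rate tied to eligibility is the minimum of 2 per year, where the distortion is negligible under the 1 SD illustration.
- A verified UTI is one that led to prescribed antibiotics. Residual inflammation and antibiotic clearance therefore occur largely in the same samples, and the net direction cannot be known.
- The exclusion applies to candidates. The plan does not say that the 2-week window is checked again on the day of the baseline sample, so even month 0 is not guaranteed clear.
- H2 is a secondary outcome in a pilot subsample.

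None of this alters the text: an entry condition that later samples lack, and a start-of-SMP value taken before exposure.

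Two stronger readings are tempting. A reader might infer three different sampling rules: screened at entry, unrestricted at month 6 and symptom-free at month 12. The documents do not support that. The symptom-free rule covers the whole first year without exempting month 6, and the month-6 sentence is merely silent. The firm contrast is entry against later.

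A reader might also conclude that the main model should adjust for a UTI or antibiotic in the previous 14 days. H1 and H3 propose that the SMP reduces both, so such a term may lie on the causal pathway and could absorb part of a real effect. Nor do the documents say that event dates are recorded; they describe counts.

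**Conclusion.** The point holds in a limited form. Two things are firm from the text. First, the month-0 WBC follows a 2-week UTI and antibiotic screen that no later sample carries, and H2 names no means of separating this from the effect of time. Second, the value standing for the SMP period is collected before any SMP use, so it cannot measure that period. The second does not depend on any assumption about WBC.

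The size of the first is not established. A reader might infer from the 7% and 37% that the baseline is biased low by a calculable amount. The documents do not support this: they give no WBC mean or SD, the elevation is assumed, the direction is open, and the symptom-free rule would lower both percentages. The effect could be negligible at 2 UTIs per year and material at one per month.

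The case for change rests on the wording of H2 and on the availability of better-matched samples at no extra collection.

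**What to change.** - **Main analysis.** In the H2 mixed model, use WBC from the monthly symptom-free samples already planned. Take those after entry, up to and including the month-6 pre-intervention sample, as usual care, and those in months 7 to 12 as SMP. State in the Intervention section that the month-6 sample falls under the symptom-free rule, so that both periods share one condition.
- **Entry sample.** Do not use month 0 as the sole baseline. Keep it for a sensitivity analysis.
- **Wording of H2.** Reconcile WBC from every sample with WBC only at timeframe starts, and the two periods described with the three contrasted.
- **Post-SMP sample.** Reconcile month 15 with the end of follow-up, and state the symptom condition under which it is taken.
- **Recent UTI or antibiotic.** Keep this indicator out of the main model. Use it at most in a sensitivity analysis, and only if event dates are recorded.

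No new samples are needed. Precision should improve: with a random intercept and independent residuals, the variance of a within-person contrast of m samples per period is 2σ²/m. Six samples per period in place of one would cut it to a sixth, an upper limit because sampling is only up to monthly. The cost is more WBC values per person to model, in irregular number. The result will also describe inflammation in symptom-free weeks only, and the plan should say so.
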